### 11.1.2 Severity

The following definitions will be used to rate the severity for any AE being collected as an endpoint/data point in the study and for all SAEs.

- Mild:** The AE is transient and easily tolerated by the patient.
- Moderate:** The AE causes the patient discomfort and interrupts the patient's usual activities.
- Severe:** The AE causes considerable interference with the patient's usual activities and may be incapacitating or life threatening.

### 11.1.3 Relationship to Pharmaceutical Product

The following definitions will be used to assess the relationship of the adverse event to the use of product:

- Reasonable Possibility** An AE where there is evidence to suggest a causal relationship between the product and the adverse event.
- No Reasonable Possibility** An AE where there is no evidence to suggest a causal

relationship between the product and the adverse event.

If no reasonable possibility of being related to product is given, an alternate etiology must be provided for the AE.

#### **11.1.4 Serious-, non Serious Adverse Event and Pregnancy Collection Period**

SAE, AE and pregnancy will be reported to AbbVie from the time the physician obtains the patient's authorization to use and disclose information (or the patient's informed consent) until 30 days or 5 half-lives following the intake of the last dose of physician-prescribed treatment, whichever period is longer.

#### **11.1.5 Adverse Event reporting**

For events from patients using and AbbVie product - notify the AbbVie contact person identified below within 5 business days of the physician becoming aware of the event.

#### **11.1.6 Serious Adverse Event Reporting**

For events from patients using and AbbVie product - notify the AbbVie contact person identified below within 24 hours of the physician becoming aware of the event.

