**Study Design:**

This is an observational, prospective, open label, single-arm, multi-centric, real-life study in HCV-positive patients (genotype 1).

The study consists of a treatment preparation phase of 4 weeks to obtain baseline physical activity by use of a wrist-worn activity tracker, a treatment phase (12 weeks) and a follow-up phase (12 weeks) to evaluate treatment response. The activity tracker is worn for 4 weeks before each visit, to obtain stable individual activity data. At every visit, questionnaire-based fatigue is recorded (FSS questionnaire), according to routine clinical care.

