**Figure 1: Study Activities**

### 9.1.1 Description of Activities

Patients will be screened to ensure they meet the inclusion criteria. All patients will be required to sign an informed consent to use and disclose personal health information. By signing this consent, patients agree to release their information to AbbVie. No study related activity will be performed prior to obtaining written informed consent.

When the investigator has determined that the patient is eligible for participation, and the patient has agreed to be included in this observational study, the patient will be handed out his personal activity tracker (ActiGraph GT9X Link [26]) (Figure 1) and will be instructed in its use. The patient will be advised to report any potential side effects related to the activity tracker, such as possible discomfort wearing the device around the clock or possible skin rash or skin irritation, to the study personnel. ActiGraph GT9X Link has a data storage capacity of 240 days/4GB. Therefore, the patient will keep the tracker for the whole duration of the study (196 days). The patients will be requested to start wearing their activity trackers on the non-dominant arm constantly for 8 weeks between visit 1 and visit 3 and for 4 weeks preceding visits 4 and 5. Everytime the patient has to put on his tracker, he will receive a reminder call from a local study personnel to increase adherence. At the last visit, the investigator will collect the tracker and deliver it to the biostatistician which in turn transfers the activity data to a post-processed environment (ActiLife 6 [27]) (Figure 1).

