## 11.1 Medical Complaints

### 11.1.1 Adverse Event Definition and Serious Adverse Event Categories

An adverse event (AE) is defined as any untoward medical occurrence in a patient, which does not necessarily have a causal relationship with their treatment. An AE can therefore be any unfavorable and unintended sign (including an abnormal laboratory finding), symptom, or disease temporally associated with the use of a medicinal product, whether or not the event is considered causally related to the use of the product.

Such an event can result from use of the drug as stipulated in the labeling, as well as from accidental or intentional overdose, drug abuse, or drug withdrawal. Any worsening of a pre-existing condition or illness is considered an AE. An AE can also derive from the medical device ActiGraph GT9X Link, which is used in this study. Minimal risks related to the Activity Tracker can be possible discomfort wearing the device around the clock and possible skin rash or skin irritation caused by the device.

Patient reported FSS questionnaire data are not considered a potential source of adverse reactions. However, participating sites should review the questionnaire data and if a possible product-related event (including a suspected adverse reaction) is noted, the Health Care Professional must determine whether the event is related to an AbbVie authorized product and if so, it should be reported to AbbVie. If an increase in the FSS score by  $\geq 1$  point is observed, the investigator must report this increased fatigue as an AE to AbbVie.

Patient derived activity tracker data are not considered a potential source of adverse reactions. Physicians are not able to see tracker data at any time. Thus, if a possible product-related event (including a suspected adverse reaction) is noted, activity tracker derived mean values of interest will be reported exclusively at the end of the study by the bio-statistician to the AbbVie PV team.

If an AE meets any of the following criteria, it is considered a serious adverse event (SAE):

---

Death of Patient:	An event that results in the death of a patient.
Life-Threatening:	An event that, in the opinion of the investigator, would have resulted in immediate fatality if medical intervention had not been taken. This does not include an event that would have been fatal if it had occurred in a more severe form.

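### Under the 30-day rule, adverse-event collection closes before the tracker's last four weeks of wear, and causality is graded only against the drug

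*Protocol*

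**What the plan says.** **Device in scope.** Protocol 11.1.1 states: "An AE can also derive from the medical device ActiGraph GT9X Link, which is used in this study". It lists discomfort, rash and skin irritation. Section 9.1.1 asks patients to tell study staff about such effects.

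**Wear schedule.** Section 9.1.1 has the tracker worn "constantly for 8 weeks between visit 1 and visit 3 and for 4 weeks preceding visits 4 and 5". The Study Design paragraph of the Abstract sets "a treatment preparation phase of 4 weeks to obtain baseline physical activity", then "a treatment phase (12 weeks) and a follow-up phase (12 weeks) to evaluate treatment response". The visit table in 9.1.2 puts V1 at Day -28, V2 at Day 1, V3 at Day 28, V4 at Day 84 and V5 at Day 168.

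**Collection period.** Section 11.1.4 makes AEs and SAEs reportable from consent until the longer of 30 days and 5 half-lives after the last dose. Footnote 1 of the visit table also starts at consent but gives 30 days only. The table marks adverse events at V5, and that mark carries footnote 1.

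**Notification.** Section 11.1.5 reads "For events from patients using and AbbVie product - notify the AbbVie contact person identified below within 5 business days", and section 11.1.6 reads "For events from patients using and AbbVie product - notify the AbbVie contact person identified below within 24 hours".

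**Causality.** Section 11.1.3 opens: "The following definitions will be used to assess the relationship of the adverse event to the use of product". Its two categories refer to the pharmaceutical product, and there is no device item.

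**Analysis.** SAP section 8, table 3.2, lists (S)AEs from V2 to V5 without a device breakdown.

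**The concern.** The drug is prescribed under routine practice, independently of the study. The tracker is the exposure that the study itself adds, so its tolerability is the safety question that belongs most directly to this protocol. The end of collection is nevertheless counted from the last dose, although the device is worn again two months later.

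A site that follows the footnote would not record a strap rash at Day 150 as an AE. A rash during treatment that is judged possibly drug-related gets no assessment against the device. In the first wear month, 11.1.4 requires reporting, but the two clauses that set the notification times describe patients who are on an AbbVie product.

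What is at stake is the completeness and attribution of device safety data. There is also some loss of explanation for dropout. Section 9.1.4 withdraws patients who do not wear the tracker for at least 3 weeks before a visit, and SAP 5.2 analyses the primary endpoint only in patients with all five visits. Skin intolerance before V5 could therefore remove a patient from that analysis with no AE record to say why.

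**Working it through.** **1. Reproduce the protocol's own figure.** V1 at Day -28 to V5 at Day 168: 168 - (-28) = 196 days = 28 weeks. This matches the 196 days in 9.1.1 and the roughly 28 weeks in 9.2.2.

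**2. Planned wear** (9.1.1 with the visit table; block boundaries taken at visit days):
- before treatment, Day -28 to Day 1: 28 days
- on treatment, V2 to V3: 28 days
- on treatment, Day 56 to 84: 28 days
- after treatment, Day 140 to 168: 28 days

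Total: 4 × 28 = 112 days.

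**3. End of collection under the 30-day rule.** With the last dose at about Day 84: 84 + 30 = Day 114. The last block starts 140 - 114 = 26 days later, so all of it is outside. Uncovered share: 28/112 = 25%. Covered share: 84/112 = 75%. If only the 3-week minimum before each visit is worn, the uncovered share is 21/84, again 25%.

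**4. End of collection under 5 half-lives.** The documents give no half-life, so h below is an assumption. End day = 84 + max(30, 5h).

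| Assumed h (days) | End day | Last-block days uncovered | Share of 112 |
|---|---|---|---|
| up to 6 | 114 | 28 | 25% |
| 8 | 124 | 28 | 25% |
| 11.2 | 140 | 28 | 25% |
| 12 | 144 | 24 | 21% |
| 14 | 154 | 14 | 12.5% |
| 16.8 or more | 168 or later | 0 | 0% |

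The thresholds are (140 - 84)/5 = 11.2 days, above which coverage of the block begins, and (168 - 84)/5 = 16.8 days, at which it is complete.

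**5. First wear month.** Consent is at V1, so Day -28 to Day 1 lies inside the period set by both 11.1.4 and footnote 1. The gap here is one of wording: 11.1.5 and 11.1.6, read literally, do not reach a patient who has not started the drug.

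**6. Off-drug share, for comparison.** (28 + 28)/112 = 50%. This follows from the wear schedule and is not the uncollected share, because the first 28 of those days are inside the collection period.

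**7. After the change in the fix.** Collection from hand-out to return at V5 covers 112 of 112 wear days.

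**The case against.** The case for leaving the text alone has several parts.

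- **Reporting duty before treatment.** A reader might infer from 11.1.5 and 11.1.6 that sites have no duty in the first wear month. The documents do not support that. Section 11.1.4 itself requires AEs and SAEs to be reported from consent. What remains is a conflict over which notification time applies before the first dose.
- **Half of wear time uncovered.** A reader might also take the 50% off-drug share as the size of the gap. It is not; the uncollected share under the 30-day rule is 25%.
- **Product complaints.** Sections 11.2.1 and 11.2.2 let a complaint arise from the tracker and give it a 24-hour clock with no drug-use condition. This stands as partial cover. However, 11.0 directs adverse events to 11.1, the examples in 11.2.1 are about damage, appearance, labelling and packaging, and the route produces no device causality grade.
- **Other places to record it.** Patients are asked to report tracker effects, handling is checked at V2 to V5, the wear sensor detects removal, and 9.1.4 records a withdrawal reason if the patient volunteers one. It would be too strong to say that a late skin reaction must go unrecorded; it has no assured place as an AE.
- **The V5 mark.** The mark can be read consistently with its footnote, as collecting at V5 the events that arose up to about Day 114. That reading confirms the gap.
- **Alternative cause.** Section 11.1.3 requires another cause when the drug is judged unrelated, and the tracker can be named there. This does not help when a drug relation is considered possible.
- **Materiality.** The device is Class I and its listed risks are described as minimal. This stands, and it limits the severity.

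**Conclusion.** The point holds, at low severity. The tracker is a declared source of AEs, but under the 30-day rule collection ends at about Day 114 and leaves out the whole wear block before V5: 28 of 112 planned days, or 25%. Causality is graded only against the drug, and the notification wording conflicts with 11.1.4 in the first wear month. Footnote 1 and 11.1.4 also give different end dates and must be reconciled.

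The 25% assumes a last dose near Day 84 and wear as scheduled. Under 11.1.4 it shrinks only if the half-life exceeds 11.2 days and vanishes only at 16.8 days or more.

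The documents give no rate of skin reactions, so the number of missed events cannot be stated. They do not support a claim that the primary estimate is affected. The effect is on the completeness and attribution of device safety data.

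**What to change.** - **11.1.4 and footnote 1 of the visit table:** state that tracker-related AEs are collected from hand-out at V1 until the tracker is returned, whatever the date of the last dose. Make the two end-date statements agree for all other events.
- **11.1.5 and 11.1.6:** replace the condition on product use with any consented patient, so that the notification times apply over the period in 11.1.4.
- **11.1.3:** add a second item, relationship to the activity tracker, with the same two categories.
- **SAP section 8, table 3.2:** show device-related AEs separately.

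The cost is a few sentences of protocol text, one extra CRF field and one table line. Sites will have a few more minor skin events to report. Treatment, visits and efficacy analyses are unchanged.

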### **11.1.7 Pregnancy Reporting**

In the event of a pregnancy occurrence in the female patient or in the female partner of a male patient, the physician will notify AbbVie contact person identified in Section 11.1.6 within 24 hours of the physician becoming aware of the pregnancy.

## **11.2 Product Complaint**

### **11.2.1 Definition**

A Product Complaint is any Complaint (see Section 11.0 for the definition) related to the biologic or drug component of the product. A Product Complaint can also derive from the medical device ActiGraph GT9X Link, which is used in this study.

For a product this may include, but is not limited to, damaged/broken product or packaging, product appearance whose color/markings do not match the labeling, labeling discrepancies/inadequacies in the labeling/instructions (example: printing illegible), missing components/product, or packaging issues.

Any information available to help in the determination of causality to the events outlined directly above should be captured.

### **11.2.2 Reporting**

Product Complaints concerning the product/ device must be reported to the Sponsor within 24 hours of the study site's knowledge of the event via local Product Complaint reporting practices. Product Complaints occurring during the study will be followed-up to a satisfactory conclusion. All follow-up information is to be reported to the Sponsor (or an authorized representative) and documented in source as required by the Sponsor. Product Complaints associated with adverse events will be reported in the study summary. All other complaints will be monitored on an ongoing basis.

Product complaints involving a non-Sponsor product / device should be reported to the identified contact or manufacturer, as necessary per local regulations.

Product Complaints may require return of the product/ device with the alleged complaint condition. In instances where a return is requested, every effort should be made by the investigator to return the product within 30 days. If returns cannot be accommodated within 30 days, the site will need to provide justification and an estimated date of return.

The description of the complaint is important for AbbVie in order to enable AbbVie to investigate and determine if any corrective actions are required.

## **12.0 Plans for Disseminating and Communicating Study Results**

At the end of this observational study, a report will be written by AbbVie or a CRO working on behalf of AbbVie. The required standard study report template will be followed. This report will contain a description of the objectives of the study, the methodology and its results and conclusions. The completed CRFs, [patient questionnaires, interim assessments], the final study output and study report are the confidential property of AbbVie and may not be released to unauthorized people in any form (publications or presentations) without express written approval from AbbVie. The study results will be submitted to local authorities per local laws and regulations.

The results of this study will be made publicly available on one of the primary registries in the World Health Organization (WHO) Registry Journal Network which meet the requirements of the International Committee of Medical Editors (ICMJE) and through scientific publications. Authorship will be in line with ICMJE' authorship requirements [\[40\]](#).

## Annex 1. ActiGraph GT9X Link [26]

The ActiGraph GT9X Link is the most sophisticated activity tracker available from the global leader in actigraphy measurement. The ActiGraph Link combines an extensively validated accelerometry measurement technology with a variety of advanced new features, including:

**Wear time sensor:** Automatically detects if a wrist worn device has been removed for simplified compliance monitoring and data cleaning.

**Programmable display:** An LCD window displays date and time, provides optional real-time subject feedback, or can be completely disabled.

The Tracker will be retrieved by the study personnel at the timepoint of study termination.

Features & Analysis	Objective Measures
LCD Screen	Raw Acceleration (G's)
Gyroscope / Magnetometer	Energy Expenditure
Heart Rate Monitoring	MET Rates
Proximity Detection	Steps Taken
Wear Time Sensor	Physical Activity Intensity
Daytime Activity	Activity Bouts
Basic Sleep Scoring	Sedentary Bouts
Inclinometer Graphing	Heart Rate R-R Intervals
Data Vault Access	Body Position
	Sleep Latency
	Total Sleep Time
	Sleep Efficiency

---

## ActiGraph GT9X Link: Regulatory Requirements

- The ActiGraph Link is a Class I medical device within the European Union that abides by the regulatory requirements listed below: EN60601-1-Medical Device General Safety Requirements
- Part 15.109 (US) – Radiated Emission Limits of Unintentional Radiators Part 15.249 (US) – Radiated Emission Limits of Intentional Radiators
- ICES-003 (Canada) – Interference Causing Equipment Standards for a Digital Apparatus.
- ActiGraph is compliant with IEC standards for “Type BF Applied Part”
- ActiGraph Link and ActiGraph wGT3X-BT is water resistant in accordance with IEC 60529 IPX7, or immersion in one (1) meter of water for up to 30 minutes.
- All ActiGraph products are manufactured Lead Free and are RoHS Compliant.

## Specifications

Dimensions	3.5 x 3.5 x 1 cm
Weight	14 grams
Sample Rate	30-100 Hertz
Dynamic Range (Primary Accelerometer)	+/- 8G
Dynamic Range (Secondary Accelerometer)	+/- 16G
Gyroscope Dynamic Range	+/- 2000 deg/sec
Magnetometer Dynamic Range	+/- 4800 micro-Tesla
Battery Life	14 days*
Data Storage	240 days / 4 GB
Communication	USB, Bluetooth® LE
Water Resistance	1 meter, 30 minutes
Wear Location	Wrist, waist
Warranty	1 year

\*Wireless disabled, 30 Hz sample rate, gyro disabled, sleep mode

## Annex 2. Fatigue Severity Scale (FSS) [38]

Below are a series of statements regarding your fatigue. By fatigue we mean a sense of tiredness, lack of energy or total body give-out.

Please read each statement and choose a number from 1 to 7, where # 1 indicates you completely disagree with the statement and # 7 indicates you completely agree.

Please answer these questions as they apply to the past **TWO WEEKS**.

	Completely Disagree						Completely Agree
1. My motivation is lower when I am fatigued	1	2	3	4	5	6	7
2. Exercise brings on my fatigue	1	2	3	4	5	6	7
3. I am easily fatigued	1	2	3	4	5	6	7
4. Fatigue interferes with my physical functioning	1	2	3	4	5	6	7
5. Fatigue causes frequent problems for me	1	2	3	4	5	6	7
6. My fatigue prevents sustained physical functioning	1	2	3	4	5	6	7
7. Fatigue interferes with carrying out certain duties and responsibilities	1	2	3	4	5	6	7
8. Fatigue is among my 3 most disabling symptoms	1	2	3	4	5	6	7
9. Fatigue interferes with my work, family, or social life	1	2	3	4	5	6	7

### Annex 3. ICD-10 Version:2016 [\[41\]](#)

#### **F32.2 Severe depressive episode without psychotic symptoms**

An episode of depression in which several of the above symptoms are marked and distressing, typically loss of self-esteem and ideas of worthlessness or guilt. Suicidal thoughts and acts are common and a number of "somatic" symptoms are usually present.

Agitated depression		single episode without psychotic symptoms
Major depression		
Vital depression		

#### **F32.3 Severe depressive episode with psychotic symptoms**

An episode of depression as described in F32.2, but with the presence of hallucinations, delusions, psychomotor retardation, or stupor so severe that ordinary social activities are impossible; there may be danger to life from suicide, dehydration, or starvation. The hallucinations and delusions may or may not be mood-congruent.

Single episodes of:

- major depression with psychotic symptoms
- psychogenic depressive psychosis
- psychotic depression
- reactive depressive psychosis

---

**Annex 5. Requirements for non-interventional studies per local laws and regulations**

- Competent Authority approval
- Competent Authority notification
- Competent Authority involvement not required
- 
- Ethics Committee approval
- Ethics Committee notification
- Ethics Committee involvement not required
- 
- Written Patient Informed Consent required:  No  Yes

Regulatory requirements, other (if applicable):

*Not applicable*

As described in the HEMATITTE study protocol (version V1.0, 09/20/2016) „... patients with Hepatitis C Virus (HCV) infection reported physical and mental fatigue as the most common symptom, highly impacting their overall quality of life. AASLD (American Association for the Study of Liver Diseases) and EASL (European Association for the Study of the Liver) guidelines therefore rate the treatment of HCV patients suffering from debilitating fatigue as a high priority. This cardinal symptom presents regardless of the stage of liver fibrosis and is difficult to quantify objectively. Similar to other potential reasons for physical fatigue, such as hepatic encephalopathy, increasing evidence suggests a direct viral impact on the central nervous system (CNS). Data demonstrating a longitudinal change of debilitating physical fatigue and increased daytime physical activity upon treatment with 3D regimen are missing to date and are anticipated by the Swiss scientific HCV community.

The rationale for this observational study is to observe the impact of therapy with 3D regimen on physical activity of HCV patients suffering from debilitating fatigue. Furthermore, this study supports the Swiss Hepatitis Strategy, which seeks for the elimination of viral hepatitis in Switzerland within the next 15 years by creating awareness for patients with extrahepatic manifestations.“

Patients included in this study applied the following criteria:

- Male or female, aged ≥ 18 years
- Treatment-naive
- Monoinfected with CHCV, GT 1 (confirmed within the last 36 months or at physicians discretion in case of risk factors)
- Non-cirrhotic (based on liver biopsy, fibroscan $\leq 9,6$ kPa and/or clinical signs)
- The decision to treat with 3D regimen is made by the physician in accordance with the local Swiss product label prior to any decision to approach the patient to participate in this study.
- Debilitating fatigue (FSS ≥ 4)
- Willing to participate in the study, and willing to wear an activity tracker.

Patients excluded from this study:

- With sources of fatigue other than HCV (especially, severe depression, cancer and hormonal disorders causing clinically significant fatigue).
- With conditions that do not allow to adhere to protocol and use of the device at investigator's discretion.
- Being wheelchair dependent.

Based on the HEMTATITE study protocol details of planned strategies for the data analysis will be documented in this SAP which will be established and finished by signatures of the statistician and the principle investigator before data base will be closed.

2 Data Sources

Data sources for the planned analyses are the data documented by the investigators on the case report forms (CRFs) for each patient. These CRFs were collected by the monitor and send to AbbVie Deutschland for electronically data collection in an OpenClinica data base.

Physical activity and sleep data will be collected by use of wrist-worn activity trackers (ActiGraph GT9X) which will be processed by device-specific software (ActiLife 6) to obtain the activity and sleep-related variables for analysis. These tracker variables will be transferred in csv format from ActiGraph to the Biostatistik – Tübingen. Dealing with and handling of the original data where described in detail in the Data Management Plan (DMP).

3 Data Management

